9.1.5.1.4 Drugs of Abuse Test

Urine will be analyzed for drugs of abuse using the provided urine testing kit.

9.1.5.2 Physical Examination

Physical examinations include assessments of general appearance, skin, HEENT (head, ears, eyes, nose and throat), chest and lungs, cardiovascular, abdomen, musculoskeletal and extremities, neurological, psychiatric and mental status.

9.1.5.3 Knee Examination

At Visit 1a both knees will be examined. From Visit 2 onwards, only the Index knee will be examined.

The subject's knee will be examined for:

- Range of motion (0-45 degrees, 46-90 degrees, 91-135 degrees)
- Presence of an effusion (Stroke Test: zero, trace, 1+, 2+, 3+)
 - Zero: No wave produced on downstroke
 - Trace: Small wave on medial side with downstroke
 - 1+: Large bulge on medial side with downstroke
 - 2+: Effusion spontaneously returns to medial side after upstroke
 - 3+: So much fluid it is not possible to move the effusion out of the medial aspect of the knee
- Crepitus on palpation with range of motion (yes/no)
- Stability of collateral ligaments (stable, mild instability, moderate instability, unstable)
- Stability of cruciate ligaments (stable, mild instability, moderate instability, unstable)

- Warmth and tenderness on palpation of the joint (yes/no)
- Skin appearance (scars, redness, bruising, swelling; all as yes/no)
- Gait (normal, mild antalgia, moderate antalgia, severe antalgia)

If the examination reveals findings that indicate a possible infection in the Index knee (e.g., the knee is red and swollen with a moderate or large effusion, or is hot and swollen with a moderate or large effusion), a blood sample will be collected for hematology testing and the subject should be referred for further specialist assessment as soon as possible. If an Index knee joint infection is suspected, this should be reported as an SAE (see Section 10.1.4 for details), and every effort should be made to retrieve documentation of the diagnosis and diagnostic procedures performed. If an Index knee finding appears to meet the criteria for further investigation and/or review by the SRC, contact the Medical Monitor (see Sections 4.3 and 4.4 for details).

9.1.5.4 Vital Signs

Vital signs include seated blood pressure (BP), heart rate (HR), respiration rate (RR) and body temperature.

Vital signs will be measured and recorded at every visit (except Visits 1b and 3). When vital signs are scheduled for the same visit as a blood sample, vital signs will be taken before the blood sample. At Visit 2, vital signs will be obtained prior to and approximately 1 hour after dosing.

Vital signs will be collected after the subject has been in a seated position for at least 5 minutes with both feet flat on the floor and the measurement arm supported so that the mid-point of the manometer cuff is at heart level. At each visit BP should be obtained using the same cuff size and the same arm. BP should be recorded to the nearest 2 mmHg mark on the manometer or to the nearest whole number on an automatic device.

9.1.6 Pharmacokinetic Assessments

9.1.6.1 Plasma

The PK of EP-104IAR will be assessed by analysis of plasma levels of FP. A validated method will be used for measuring FP in the blood. Detailed instructions on the collection, processing, handling and shipping of plasma samples will be provided in the Laboratory Manual.

9.1.6.2 Used Injection Kits

Empty vials and syringes used to administer EP-104IAR will be retained after administration and stored at the site according to the instructions in the IMP Handling Manual until drug accountability has been completed. After this time, they will be shipped to the bioanalytical laboratory for residual drug analysis to calculate the delivered dose for each subject. The timing of drug accountability visits will be detailed in the Clinical Monitoring Plan.

9.1.7 Efficacy Assessments

Efficacy will be assessed using several patient-reported outcome measures and the MDGA. The following patient-reported measures will be collected using the ePRO device: WOMAC Index, NPRS, rescue medication / non-drug therapy, and physical activity levels.

The PtGA and SF-36 measures will be collected using an ePRO module in the site eCRF.

9.1.7.1 WOMAC® Index

The WOMAC® Index (Version 3.1, 11-point numeric rating scale (NRS), 24-hour recall) is a disease-specific, self-reported measure to assess pain, stiffness and physical function in subjects with knee OA. It consists of 24 items divided amongst 3 subscales to evaluate pain, stiffness and physical function ([Bellamy, 2005](#)).

- The Pain subscale evaluates pain associated with OA of the Index knee during walking, using stairs, in bed, sitting or lying, and standing.
- The Stiffness subscale evaluates stiffness associated with OA of the Index knee after first walking and later in the day.
- The Physical Function subscale evaluates physical function related to stair use, rising from sitting, standing, bending, walking, getting in/out of a car, shopping, putting on/taking off socks, rising from bed, lying in bed, getting in/out of bath, sitting, getting on/off toilet, heavy household duties, and light household duties.

The WOMAC Index is a reliable, valid and sensitive measure of disability associated with OA of the knee. An electronic version of the questionnaire will be completed by the subject using the ePRO device.

[figure not shown]
- The WOMAC Pain subscale, will be completed **weekly**, preferably in the **morning**.
 - During the Washout and Baseline period WOMAC Pain will be recorded for both knees
 - From Visit 2 onwards WOMAC Pain will be recorded for the Index knee
- The full WOMAC Index (Pain, Physical Function and Stiffness subscales) will be completed at Visit 2 (pre-dose) and then **monthly** (every 4 weeks), preferably in the **morning** for the Index knee.

Subjects will be asked to refrain from using rescue medication in the 12 hours prior to completing the WOMAC questionnaire whenever possible. The ePRO device will provide a reminder and will ask if the subject complied e.g. “Did you use any rescue medication in the last 12 hours?” (Yes/No). The WOMAC questionnaire will be completed regardless of the subject’s response.

9.1.7.2 NPRS – Numerical Pain Rating Scale

Subjects will rate their daily Index knee pain throughout the study using the NPRS. During the Washout and Baseline Period this question will be asked separately for each knee. From Visit 2 onwards NPRS scores will only be collected for the Index knee. Subjects will enter scores each **evening** directly into the ePRO device provided.

[figure not shown]
The question for the subject is: “How was your pain level in your (right/left) knee over the past 24 hours?

9.1.7.3 PtGA – Patient Global Assessment of Arthritis

The subject will assess his/her current disease activity using the PtGA NRS (0-10), where 0 equals “Very Good” and 10 equals “Very Poor”.

The question for the subject is: “Considering all of the ways your arthritis in your left/right knee affects you and your life, how are you doing today?”

Scores will be completed by the subject in the eCRF at the site.

9.1.7.4 SF-36 Health Survey

The SF-36 Health Survey Version 2 (Acute, 1-week recall) is a widely used patient-based generic quality-of-life questionnaire containing 36 items measuring health in 8 domains (Ware & Sherbourne, 1992). These include physical functioning, role limitations due to physical health problems, role limitations due to emotional problems, social functioning, vitality, mental health, bodily pain and general health perceptions. The questionnaire will be completed by the subject using the eCRF at the site.

9.1.7.5 Rescue Medication/Non-Drug Therapy

Subjects will be required to record their use of rescue medication using the ePRO device. A daily question “Did you use any of the provided rescue medication over the past 24 hours?” (Yes/No) will be asked each **evening**.

If yes, a follow-up question on whether rescue medication was used to treat pain in the Index knee will also be asked. E.g., “Did you use the provided rescue medication to treat pain in your affected knee?” (Yes/No)

Subjects will not be required to record the number of pills used each day. Instead, the site's accountability/pill counts will be entered into the eCRF and will be used to calculate an approximate average number of pills used per day and/or per week, over the study period. Subjects will be asked to refrain from using rescue medication in the 12 hours prior to completing the WOMAC questionnaire whenever possible.

Using the ePRO device, subjects will also be asked to record:

- the use of other pain medications. A daily question "Did you use any other pain medications over the past 24 hours for any reason?" (Yes/No) will be asked each **evening**.
- the use of any non-drug rescue therapies. A daily question "Did you use any Physiotherapy or heat/cold compresses over the past 24 hours?" (Yes/No) will be asked each **evening**.

9.1.7.6 Physical Activity Levels

Subjects will be asked to evaluate their level of physical activity using the ePRO device. A daily question "How would you describe your level of physical activity today?" (Low/Moderate/High) will be recorded each **evening**.

9.1.7.7 MDGA-Physician's Global Assessment of Arthritis

This measurement is intended to capture the Investigator/blinded assessor's clinical opinion based on the entirety of information available at each visit. e.g., the Investigator/blinded assessor can consider the subject's reported OA symptoms by asking "How is your knee pain and stiffness today?" or "How is your knee feeling today?", review the PtGA, and review any AEs or knee examination findings that might indicate a change in disease activity/severity.

The Investigator/blinded assessor will assess the subject's current disease activity using the NRS (0-10), where 0 equals "None" and 10 equals "Very Severe".

The question is: "How would you describe the patient's disease activity today?"

0	1	2	3	4	5	6	7	8	9	10
										
None	Mild	Moderate			Severe			Very Severe		

9.1.8 Exploratory Assessments

9.1.8.1 Question on Treatment Received

Following completion of all other safety, PK and efficacy assessments at Visit 9 (End of study/Early-Exit Visit) the subject and the blinded assessor will each be asked the following question:

“Do you think (you/the subject) received the test medication or the placebo?” (Test medication / Placebo)

Why do you think this (check all that apply)?

- Knee pain
- Knee function
- Knee stiffness
- Quality of life
- Adverse effects
- Other (specify) _____

The responses to this question may be useful when interpreting any unusual or unexpected physician or patient-reported outcome measures.

9.2 Schedule of Assessments

For a detailed schedule of assessments (including all protocol required assessments, visits and visit windows) please refer to the [Schedule of Events](#).

9.2.1 Visit 1a and Visit 1b: General Screening (Day -56 to -15)

[figure not shown]
Informed consent will be obtained prior to performing any study related procedures or assessments.

Site staff will be trained in methods of approaching and speaking to potential study subjects in a manner that conveys a neutral expectation of treatment effectiveness.

After signing the informed consent, the following data will be collected and study procedures will be performed per [Schedule of Events](#), to assess subject eligibility for the study:

- Demographics (birthdate (month/year), age, sex, race, ethnicity, height, weight, BMI).
- OA history (to be confirmed by review of medical records if possible).
- Medical and surgical history.
- Prior and concomitant medication (conmed) use, including the subject's reported response to prior OA treatments.
- Vital signs.
- Physical examination including knee exam in both knees.
- In-clinic patient-reported score of typical OA knee pain when not using medication.

- Subjects will be asked separately for each knee: “What is your typical level of knee OA pain in your left/right knee when you do not use pain medication?

- Blood samples for safety laboratory analysis (hematology, clinical chemistry, pregnancy testing and HbA1c).
- An ACTH stimulation test. This test may be performed at any time during Screening, including at Visit 1b.
- Urine samples for safety urinalysis and drugs of abuse testing.
- X-rays will be collected and reviewed centrally to evaluate OA severity for eligibility purposes using the Kellgren-Lawrence grading scale.
 - If an x-ray from within the past 6 months is not available in the subject’s medical records, a new one will be performed.
 - If both knees are potentially eligible at Screening, an x-ray of both knees should be performed to help identify the Index knee.
- During Screening (Visit 1a or 1b) potential subjects will receive training and information about clinical trials, placebo/vehicle control, the placebo response and the importance of accurately reporting their pain and symptoms.

9.2.2 Visit 1b: Initiate Washout & Baseline (Day -15, window -2 days)

Subjects will be instructed how to begin washout of their current pain medications and will be trained in the use of the ePRO device.

Subjects will be provided with a bottle of rescue medication (acetaminophen/paracetamol) to be used (if needed) during the study and the rules around use and recording of rescue medication will be explained.

9.2.3 Washout and Baseline Period (Day -14 to -1, window -2 days)

Following Visit 1b, subjects will begin a 2-week Washout and Baseline Period, from which their baseline and qualifying pain will be determined. Subjects taking disallowed pain medications will be required to washout during this period. Subjects will be instructed to begin recording their daily and weekly measurements using the ePRO device provided at the start of this period and will continue recordings until the end of the study.

Daily and weekly measurements will be collected during this entire period and will be used to determine eligibility, as described below.

Daily pain scores in each knee will be recorded using the 11-point NPRS. **Daily** questions on rescue medication usage, non-drug rescue therapies and physical activity levels will also be completed. Subjects will be reminded to answer these questions at approximately the same time each day, in the **evening** before retiring.

Weekly scores in each knee will be recorded preferably in the **morning** using the WOMAC Pain subscale.

Eligibility for randomization at Visit 2 will be calculated based on:

- Number of daily pain recordings (each knee).
 - Subjects must complete at least 5 out of 7 of the daily NPRS scores in each week of the Washout and Baseline Period.
- The two WOMAC Pain subscale scores in the Index knee (collected at the end of each week of the Washout and Baseline Period).
 - Subjects must complete both weekly WOMAC Pain subscales for the Index knee.
 - The WOMAC Pain subscale comprises 5 questions each scored 0-10. The 5 scores are added together and divided by 5 to give a composite score out of 10.
 - The 2 composite scores must each be ≥ 4.0 and ≤ 9.0 .
 - The 2 composite scores must not differ (vary) by more than 3 points.
- The two WOMAC Pain subscale scores in the non-Index knee (collected at the end of each week of the Washout and Baseline Period).
 - The 2 composite scores are both ≤ 6.0 .

If a Subject fails to complete scheduled assessments during the Washout and Baseline Period for reasons outside their control (e.g., technical issues or a misplaced, lost, or broken ePRO device) and is willing to continue in the study, the Sponsor may agree (at their discretion) to the subject re-starting the 2-week Washout and Baseline Period if it can be completed within the 8-week Screening period.

9.2.4 Visit 2: Baseline and Dosing (Day 1)

9.2.4.1 Pre-Dose Procedures

Subjects will return to the site once the Washout and Baseline Period is complete. Subjects will be required to bring their ePRO device and any unused rescue medication to the site.

Following review of eligibility and Index knee selection, qualified subjects will be randomized to receive a single IA injection of EP-104IAR or vehicle control in their Index knee.

In addition to confirming eligibility, **pre-dose activities** include:

- Blood samples for hematology, clinical chemistry, cortisol and PK analyses.
- Urine collection for safety urinalysis, pregnancy test and drugs of abuse.
- Vital signs.
- Physical exam.
- Exam of Index knee.
- Weight.
- PtGA.
- MDGA.
- WOMAC Index.
- Health status (SF-36).
- Recording changes in procedures or conmed use.

Imaging Sub-Study

Subjects who volunteer to participate in the imaging sub-study will have a separate visit for baseline MRI to be performed prior to all pre-dose activities listed above.

The baseline MRI can occur on a separate day but must be within 5 days before dosing.

For women of childbearing potential, the pre-dose urine sample for pregnancy testing will be collected prior to the baseline MRI to confirm eligibility for the MRI scan. This does not need to be repeated prior to dosing

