Subjects will be trained in the use of the ePRO device. Subjects will be provided with a bottle of rescue medication (acetaminophen/paracetamol) to be used (if needed) during the study and the rules around use and recording of rescue medication explained.

Washout and Baseline Period

Subjects will complete a 2-week period, in which their baseline (and qualifying) pain will be determined. Subjects taking disallowed pain medications will be required to washout during this period. Subjects will record their daily and weekly measurements using the ePRO device provided at the start of this period.

The daily and weekly measurements collected during this period will be used to determine eligibility (and if applicable, help identify the Index knee).

Baseline and Dosing – Visit 2 (Day 1)

Pre-Dose Activities

Subjects will return to the site once the Washout and Baseline Period is complete. Following review of the data on the ePRO device and confirmation of eligibility, qualified subjects will be randomized to receive a single injection of EP-104IAR or vehicle control in their Index knee.

If both knees are potentially eligible the Index knee will be selected based on the criteria in Section 9.1.3.2.

Baseline safety, PK and efficacy assessments will be performed prior to dosing, including the full WOMAC Index (for the Index knee), Patient's Global Assessment of Arthritis, Physician's Global Assessment of Arthritis and the Short Form 36 health survey.

Imaging Sub-Study

Subjects in the imaging sub-study will have a baseline MRI performed.

Once the Index knee is selected, subjects in the imaging study will receive a baseline MRI. The baseline MRI will be performed prior to all other pre-dose safety, PK and efficacy assessments. If the MRI is performed on a separate day to the other assessments, it should be scheduled to occur within 5 days of dosing. For women of childbearing potential, a urine pregnancy test must be performed prior to performing the MRI. The pregnancy test does not need to be repeated prior to dosing

Dosing Procedure

As EP-104IAR is visibly different from the vehicle control, an unblinded individual will administer the injection. Subjects will be blinded to treatment by shielding their view of the filled syringe and the injection field during the procedure. All other assessments will be performed by blinded site staff.

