11 A serum pregnancy test will be performed on all women of childbearing potential at Screening. The sample collected for clinical chemistry analysis may be used for this purpose. A urine pregnancy test will be performed on all women of childbearing potential at Visit 2 and the End-of-Study (or Early Exit) visit. If the subject is participating in the optional imaging sub-study, the Visit 2 urine pregnancy test will be performed prior to performing the MRI. It does not need to be repeated prior to dosing.

12 HbA1c will be measured at Screening and End-of-Study (or Early Exit) visits.

13 To be collected at approximately the same time each visit, between 7-11 a.m. The clinical chemistry sample can be used for cortisol analysis, if being collected at the same visit.

14 Prior to and 2 hours after dosing. (For the 2 hour post-dose assessment a -15/+15-minute window is permitted.)

15 The ACTH stimulation test may be performed at any time of day and on any day during Screening, including at Visit 1b.

16 If the morning serum cortisol test result at Visit 6 (Week 8) is <350 nmol/L (<12.7 µg/dL) an ACTH stimulation test is to be performed at Visit 7 (Week 12). The site will be notified of this requirement in advance of the subject attending this visit.

17 For subjects whose ACTH stimulation test was abnormal at Visit 7, the test will be repeated at the End-of-Study (or Early Exit) Visit (the site will be notified of this requirement in advance of the subject attending this visit).

18 For those subjects not undergoing the ACTH stimulation test at Visit 9 (Week 24/Early Exit) if the result of the morning serum cortisol test at this visit is <350 nmol/L (<12.7 µg/dL), the site will be informed that an unscheduled visit is required to perform an ACTH stimulation test.

Notes:
ACTH=Adrenocorticotrophic hormone; AEs=Adverse events; Chem=Blood chemistry panel; Commed=Concomitant medication; ePRO=Electronic patient-reported outcome; Hem=Blood hematology panel; MDGA=Physician's Global Assessment of Arthritis; MRI=Magnetic resonance imaging; NPRS=Numerical pain rating scale; OA=Osteoarthritis; PK=Pharmacokinetic; PIgA=Patient's Global Assessment of Arthritis; SF-36=Short Form 36 questionnaire; WOMAC=Western Ontario and McMaster Universities Osteoarthritis Index.

IMAGING SUB-STUDY ADDITIONAL SCHEDULE OF EVENTS

Visit	1a Screening (Multiple days)	2 Baseline & Dosing	7	9 End-of-Study (or Early Exit Visit)	10 Imaging Follow-up
Study Week	-8 to -3	1	12	24	52

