5.3 Exclusion Criteria

1. OA of the Index knee due to acute injury or trauma that occurred within 12 months prior to Screening, or unstable joint (such as a torn anterior cruciate ligament) within 12 months of Screening.
2. X-ray evidence of chondrocalcinosis likely to affect the outcome of this study in the opinion of the investigator.
3. Diagnosed or suspected ipsilateral hip OA.
4. Knee pain that is not clinically attributable to OA of the knee (e.g., radicular low back pain or hip pain that is referred to the knee that could cause misclassification).
5. Any other disorders that, in the Investigator's opinion, impact mobility, strength or sensation, or are a co-existent source of pain or inflammation that interferes with the subject's ability to assess their knee OA pain and function (e.g., fibromyalgia, painful diabetic neuropathy, low back pain, rheumatic disorders such as rheumatoid arthritis, other autoimmune diseases, ankylosing spondylitis, reactive arthritis (aka Reiter's syndrome), psoriatic arthritis, gout, etc.).
6. Presence of other symptoms or conditions in the Index knee that would confound evaluation of pain and other functional assessments of knee OA (e.g., a symptomatic popliteal cyst (Baker's cyst)).
7. History of infection in the Index knee within 9 months prior to Screening, or clinical signs and symptoms of an active infection in the Index knee at Screening or Baseline Visits.
8. Total/Partial Knee Replacement for the Index knee, or any other surgery (including arthroscopy) for the Index knee within 12 months prior to Screening, or planned surgery during the study.
9. Total/Partial Knee Replacement Surgery of the non-Index knee within 6 months prior to Screening, or planned surgery (in any location) during the study that would require use of a restricted medication during the study.
10. IA injection of corticosteroids in any joint within 3 months prior to Screening, or IA injection of extended-release corticosteroids in any joint within 6 months prior to Screening.

11. IA injection in the Index knee of platelet rich plasma or other prolotherapy (e.g., dextrose) within 3 months prior to Screening, or hyaluronic acid within 6 months prior to Screening.
12. Oral, IV or intramuscular corticosteroids for any indication within 30 days prior to Baseline; or planned used during the study.

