13. Inhaled or intranasal corticosteroids, or expected need for these, for any indication from the start of the Washout and Baseline Period until at least 4 Weeks post-dose.
14. Any topical corticosteroids applied to the Index knee, or expected need for these, from the start of the Washout and Baseline Period until 24 Weeks post-dose, or planned use of restricted topical corticosteroids (on any location) during the study (restricted medications are listed in Protocol Section [8.1.2](#)). Intravitreal corticosteroids are permitted with no restrictions.
15. Use of any long-acting opioids within 30 days prior to Screening, or use of any opioids (including tramadol and tapentadol) more than twice per week within 30 days prior to Screening and from which the subject is unwilling or unable to washout.
16. Presence or history of substance abuse, including but not limited to, opioids and marijuana. Current use of marijuana for any reason is also exclusionary.
17. Positive urine drug test at Screening or Baseline Visits that is not explained by the use of prescription medications permitted during the study. A positive urine drug test without a valid prescription that accounts for the result is automatically exclusionary and cannot be repeated.
18. Presence of alcohol abuse or dependence or drinking more than 21 units of alcohol per week (i.e., 3 drinks per day): 1 unit = 150 mL of wine, 360 mL of beer or 45 mL of 40% alcohol); or history of alcohol abuse judged by the Investigator as likely to recur during the study.
19. Current use of systemic immunosuppressive therapy; or use within 6 months prior to Screening.
20. Unwilling or unable to washout of any prohibited medications and not use them for the duration of the study (Washout and Baseline Period to End-of-Study Visit). Prohibited medications are listed in Section [8.1](#).
21. Use of another investigational drug or device within the 30 days prior to Screening, or an investigational biologic within the 60 days prior to Screening, or current/planned participation in another interventional trial during this study.
22. A history of sarcoidosis or amyloidosis.
23. A history of osteomyelitis.
24. A history of or active Cushing's syndrome.

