25. Currently has or is receiving treatment for the following conditions: psychotic disorder, bipolar disorder, symptomatic depressive or anxiety disorders. Mild or well-controlled psychiatric disorders (e.g., mild depression) are permitted if the medication used is not prohibited by the protocol (see Section 8.1).
26. At Screening, a baseline serum cortisol value ≤ 138 nmol/L (≤ 5 μ g/dL) from the ACTH stimulation test, or an abnormal ACTH stimulation test result.
27. Currently has diagnosed insulin-dependent diabetes mellitus or poorly controlled non-insulin dependent diabetes mellitus (defined as a hemoglobin A1c (HbA1c) value of $\geq 8.0\%$ (64 mmol/mol) at Screening.
 - Pre-diabetics (i.e., HbA1c levels between 5.7-6.4% (39-46 mmol/mol) at Screening) and well-controlled non-insulin dependent diabetics (i.e., HbA1c levels $\leq 7.9\%$ (63 nmol/mol) at Screening) are permitted.
28. Diagnosed hepatic or renal disease, or the following laboratory values at Screening: aspartate aminotransferase (AST) or alanine aminotransferase (ALT) $> 3 \times$ upper limit of normal (ULN); bilirubin $> 2 \times$ ULN (unless isolated Gilbert's syndrome); serum creatinine $> 1.5 \times$ ULN.
29. Current malignancy of any type, or history of a malignancy within 12 months prior to Screening (other than resected basal cell carcinoma, squamous skin cell carcinoma, or resected cervical atypia or carcinoma in situ).
30. Any infection requiring IV antibiotics within 4 weeks of the Baseline Visit, or oral antibiotics within 2 weeks of the Baseline Visit.
31. Known active or quiescent systemic fungal, bacterial (including tuberculosis), viral or parasitic infections, or ocular herpes simplex.
32. Known or clinically suspected infection with human immunodeficiency virus, hepatitis B or C viruses.
33. Skin breakdown on the Index knee where the injection will take place.
34. Females who are pregnant, lactating, or who have a positive pregnancy test result at Screening or Baseline Visits.
35. Known or suspected hypersensitivity or contraindication to any of the ingredients in the investigational medicinal product, including carboxymethyl cellulose and polysorbate 80, to fluticasone propionate or any other corticosteroids (for example cortisol-related endocrinopathy), or to lidocaine (if used during IA injection procedure).
36. Known or pending disability or workers' compensation claims.
37. Previous randomization and treatment in this study.

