9.1.4 Selection of the Index knee

For subjects who present with two potentially eligible knees at Screening it will be necessary to identify which knee is the Index knee (the Index knee is the knee in which IMP/vehicle control is to be administered and all efficacy and safety assessments are performed from Visit 2 onwards).

Selection of the Index knee will occur prior to randomisation at Visit 2, following final review of all eligibility criteria. To aid the sites in their review of eligibility criteria and selection of the Index knee, the ePRO devices will provide a summary of the Washout and Baseline diary entries for each knee, including (at minimum) the number of daily and weekly pain recordings and the Weekly WOMAC Pain scores. The criteria in [Table 6](#) below will be used to help select the Index knee.

If both knees meet all the criteria for the Index knee and do not exceed the maximum permitted WOMAC Pain subscale scores for the non-Index knee, then the worst knee is selected as the Index knee. If the WOMAC Pain scores are the same in both knees, the Investigator may select either knee as the Index knee in consultation with the Subject.

Table 6 Criteria for Selecting the Index knee in Subjects with a Diagnosis (or Symptoms) of Bilateral Knee OA at Screening

Criteria	Index Knee	Non-Index Knee
Diagnosis of primary OA of the knee (per ACR clinical and radiological criteria)	Required	Not required
	AND	AND
Subject reports OA symptoms present at least 6 months prior to Screening	Required	Not required
	AND	AND
Kellgren- Lawrence Grade	2 or 3	Not required
	AND	AND
Both WOMAC Pain subscale scores in the Washout & Baseline Period	≥ 4.0 to ≤ 9.0 (out of 10) and do not vary by >3 points	≤ 6.0 (out of 10)

Notes: ACR=American College of Rheumatology; OA=osteoarthritis; WOMAC=Western Ontario and McMaster Universities Osteoarthritis Index

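### The baseline contrast MRI is scheduled before the Visit 2 urine drug test, so an imaging volunteer can receive gadolinium and then be excluded under criterion 17

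*Protocol*

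**What the plan says.** Protocol Section 9.2.4.1 lists the Visit 2 pre-dose activities. They include urine collection for drugs of abuse, examination of the Index knee, and recording of changes in concomitant medication. It then says that sub-study volunteers "will have a separate visit for baseline MRI to be performed prior to all pre-dose activities listed above". The scan may be on a separate day, within 5 days before dosing. The Synopsis and Section 4.1 give a similar order: "The baseline MRI will be performed prior to all other pre-dose safety, PK and efficacy assessments". Section 9.1.3.2 confirms that the baseline scan uses an intravenous gadolinium agent.

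Exclusion 17 (Section 5.3) applies at Baseline as well as at Screening: "A positive urine drug test without a valid prescription that accounts for the result is automatically exclusionary and cannot be repeated".

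One Visit 2 test is explicitly moved ahead of the scan. Footnote 11 of the Schedule of Events says that, in the sub-study, "the Visit 2 urine pregnancy test will be performed prior to performing the MRI", and that it need not be repeated before dosing.

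Two other statements bear on the order. Section 9.1.4 says: "Selection of the Index knee will occur prior to randomisation at Visit 2, following final review of all eligibility criteria". The Synopsis says: "Once the Index knee is selected, subjects in the imaging study will receive a baseline MRI". Read together, they put the full eligibility review before the MRI.

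**The concern.** The drug test is an eligibility test at Visit 2, and Section 9.2.4.1 puts it after the contrast injection. A volunteer with a new, unexplained positive would be excluded only after the scan.

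That scan would yield nothing. Section 11.8.1.1 compares later scans with baseline, and SAP Section 3.4.4 limits the MRI population to randomized subjects. The volunteer would have had a research-only exposure without contributing data. Section 2.2 describes contrast effects as usually mild to moderate and transient, but also mentions very rare severe or fatal hypersensitivity reactions. An exposure with no return is worth avoiding where a test already in the schedule can prevent it.

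The sections also give sites two incompatible instructions about what must be known before the scan.

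**Working it through.** The plan gives no figure to reproduce. The check sets the sections side by side and adds two small day counts.

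1. **Order as written.** Combining the Synopsis and Sections 4.1, 9.1.4 and 9.2.4.1:
   - eligibility review and Index-knee selection;
   - imaging exclusions, eGFR and, where applicable, the pregnancy test;
   - contrast MRI;
   - urine drug test, formal knee examination and the other listed activities;
   - randomization, which Section 4.1 places after all pre-dose assessments;
   - dosing.

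2. **Which section settles the place of the drug test.** Section 9.2.4.1 does so, because it names drugs-of-abuse urine in the list that the scan precedes. The Synopsis and Section 4.1 are less decisive. They refer to safety, PK and efficacy assessments. The drug test is filed under Safety Assessments (9.1.5.1.4), but the Schedule of Events lists its sample separately from the urine sample for safety.

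3. **Whether the eligibility review cures the order.** Section 9.1.4 requires review of all criteria before Index-knee selection, and the Synopsis puts selection before the scan. Criterion 17 needs the Baseline result. If 9.2.4.1 is followed, that result does not exist at the time of the review. Either the review is incomplete or 9.2.4.1 is not followed. This is a conflict between sections and does not remove the exposure.

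4. **Exclusions that depend on a listed test result falling after the scan.** One: criterion 17.

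5. **Age of the Screening result at Visit 2.** Section 9.2.1 places Screening at Day -56 to Day -15, and dosing is on Day 1. The schedule runs from Day -1 to Day 1, so there is no Day 0.
   - Earliest: 1 - (-56) - 1 = 56 days.
   - Latest: 1 - (-15) - 1 = 15 days.
   - A new positive would have to arise within these nominal 15 to 56 days.

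6. **Age of the drug result at dosing if the test moves ahead of the scan.**
   - Same-day MRI: 0 days.
   - Separate-day MRI: at most 5 days, from the stated window.
   - In practice it is fewer. The second weekly WOMAC Pain score is needed to select the Index knee, and Section 9.2.3 collects it at the end of the second week of a period running from Day -14 to Day -1. On nominal days a Day -5 scan would precede that score.

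**The case against.** The strongest reply is that the protocol already puts eligibility first. Section 4.1 opens Visit 2 with a final eligibility review and knee selection before it mentions the MRI, and Section 9.2.4.1 treats confirming eligibility as additional to its list. If Section 9.1.4 governs, criterion 17 is settled before the scan. This shows that the intended order may be sound. It does not tell a site to run the kit before the scan, and the one section that places the drug test places it afterwards.

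A reader might infer that the knee criteria are stranded in the same way, because the formal Index-knee examination is also on the later list. The documents do not support that. Criterion 7 concerns "clinical signs and symptoms of an active infection in the Index knee at Screening or Baseline Visits" and criterion 33 "Skin breakdown on the Index knee where the injection will take place". Both are clinical observations. Neither is tied to the formal examination in Section 9.1.5.3, and the eligibility review can make them before the scan. The protocol only leaves unsaid that it should.

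A reader might also infer that contrast is given without adequate checks. That is not so. The imaging exclusions, including allergy and eGFR, and the pregnancy test all precede the scan, and the sub-study is optional with separate consent. A positive drug test is not among the imaging-specific exclusions. The issue is a wasted exposure and does not involve a known contraindication to contrast.

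The objection that no rate is shown also stands. The documents give none.

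**Conclusion.** The point holds in a narrow form: the written order allows a volunteer to receive gadolinium and then be excluded under criterion 17, and it conflicts with the sections that put eligibility review before the scan. One criterion is affected.

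The number of subjects is unknown. It is probably small, because an affected person must have joined an optional sub-study, passed the Screening drug test, and then had a new unexplained positive. The main efficacy and safety analyses are unaffected: the exclusion comes before randomization and dosing, which the SAP's ITT and Safety populations require.

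This is a minor, cheap improvement. The conclusion assumes that sites follow Section 9.2.4.1 literally. The usefulness of the fix assumes that the urine kit supplied under Section 9.1.5.1.4 can be read before the scan, since no turnaround time is stated.

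**What to change.** Amend Section 9.2.4.1, and align the Synopsis and Section 4.1, so that for sub-study subjects:

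- the urine drug kit is run before the contrast MRI, at the same time as the pregnancy sample where one is taken;
- the pre-MRI eligibility review explicitly includes a look at the Index knee for signs of infection and skin breakdown (criteria 7 and 33);
- all other pre-dose assessments, including the formal Index-knee examination and the concomitant-medication update, stay on the dosing day as already scheduled.

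The cost is protocol wording, matching imaging instructions and a little site scheduling. No new test is added. The downside is that, with a separate-day scan, the drug result can be up to 5 days old at dosing, in practice fewer. The protocol already accepts the same ageing for the pregnancy test.

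The change reduces late exclusion but does not eliminate it. A new knee finding on the dosing day, or use of a prohibited or restricted therapy (Section 8.1) that comes to light that day, could still exclude someone who has had contrast.
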